## **14. STATISTICAL METHODS**

### **14.1. General Considerations**

Statistical Analysis will be undertaken by the sponsor or under the authority of the sponsor. A general description of the statistical methods to be implemented in this clinical trial is outlined below. More details will be included in the stand-alone Statistical Analysis Plan (SAP). The SAP will be developed and finalized prior to database lock.

All data summaries and statistical analyses will be performed using the Statistical Analysis System (SAS) software Version 9.4 or higher (SAS Institute, Cary, NC). Throughout the analysis of data, the results for each subject/eye will be used when available for summarization and statistical analysis. Unscheduled visits will be summarized separately and will be excluded from the statistical analysis.

Summary tables (Descriptive statistics and/or frequency tables) will be provided for all baseline variables, efficacy variables and safety variables as appropriate. Continuous variables will be summarized with descriptive statistics (n, mean, standard deviation [SD], median, minimum and maximum). Frequency count and percentage of subjects or eyes within each category will be provided for categorical data.

Summaries will be presented by separately for each time point (Baseline, fitting, 3-Day follow-up, 1-week follow-up) and will be performed separately by completion status (Safety Population, Per-Protocol Population or Intent-to-treat, when appropriate).

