### Slit Lamp Findings (SLF)

Slit Lamp Findings (Grade 3 or higher) will be assessed for each subject eye at all study visits (schedule and unscheduled). SLFs will be evaluated and classified using the FDA Grading scale rating from 0 to 4, where Grade 0 represents the absence of findings and 1 to 4 representing successively worse findings (i.e. Grade 1=trace, Grade 2= mild, Grade 3=moderate and Grade 4= severe). The percentage of eyes with Grade 3 or higher slit lamp findings will be analyzed and will include corneal infiltrates. See [REDACTED] in Appendix H for more details on the collect of SLFs.

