### Unacceptable Lens Fit

Unacceptable lens fit will be assessed at all study visits (scheduled and unscheduled) for each subject eye. Unacceptable fit is a binary response where Y=1 if lens fit is unacceptable and Y=0 otherwise. Unacceptable fit was defined as unacceptable if any one of the following criteria:

- limbal exposure at primary gaze or with extreme eye movement;
- edge lift;
- excessive movement in primary up gaze;
- insufficient movement in all three of the following conditions: primary gaze, up gaze, and push up test.

Eyes with multiple unacceptable fitting events was counted only once. See [REDACTED] in Appendix H for additional details regarding lens fit assessments.

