## 2.3. Hypotheses

### Co-Primary Safety Hypotheses

1. When wearing the Test lenses, the proportion (%) of eyes with at least one reported clinically significant slit-lamp finding (Grade 3 or 4) during the post-fit period will be statistically less than 5%.
2. When wearing the Test lenses, the proportion (%) of eyes with an unacceptable fit during the study will be statistically less than 5%.

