### 7.3. Unscheduled Visits

If, during the investigation, a subject requires an unscheduled visit to the clinical site, the following information will be collected, as appropriate:

- Chief complaint prompting the visit. If the reason is an adverse event, the applicable eCRF for the adverse event must be completed and subject record completed as appropriate.
- Date and time of the visit and all procedures completed at the unscheduled visit.
- Review of adverse event and concomitant medications.
- Documentation of any test article dispensed or collected from the subject, if applicable.
- Slit lamp findings (using the Slit Lamp Classification Scale).

If the Investigator withdraws a subject from the study, the final study visit case report forms must be completed indicating the reason(s) why the subject was withdrawn. The subject record must be completed documenting the date and primary reason for withdrawal and the study CRA notified.

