# Clinical Study Protocol

## Johnson & Johnson Vision Care, Inc.

Table 7: Historical Data by Endpoint

Endpoint Type	Endpoint	Data Type	Value
*Primary Efficacy	VP - Distance	Mean (SD)	-0.109 (0.0848)
	VP - Intermediate		-0.024 (0.1129)
	VP - Near		0.085 (0.1264)
	CLUE Vision (Hyperopes)		57.1 (17.27)
	CLUE Vision (Myopes)		60.6 (16.84)
**Primary Safety	Grade 3 + SLF (Adverse Event)	Rate	0.24% (1 eye)
	Unacceptable Lens Fitting		0% (0 eye)
*Secondary	CLUE Vision Hyperopes	Mean (SD)	57.1 (17.27)
	CLUE Vision Myopes		60.9 (16.65)
	CLUE Comfort (Hyperopes + Myopes)		72.3 (17.43)
	CLUE Handling (Hyperopes + Myopes)		71.7 (17.09)
	Lens Fit Success	Rate	100%

VP: Visual Performance, SD=Standard Deviation

\*Summaries for primary efficacy and secondary endpoints were provided for the per-protocol population at the 1-week follow-up evaluation for period 1 only.

\*\* Summaries for the primary safety endpoints were provided for the safety population; all available data was included

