#### **The Model:**

Let  $Y_1$  and  $Y_2$  denote the binary outcomes of lens fit acceptance (Yes/No) in left and right eyes, respectively, across dispensing and follow-up visits when wearing the Test lens. Considering the correlation,  $\rho$ , between  $Y_1$  and  $Y_2$ , the distribution of the sum  $Y = Y_1 + Y_2$  is obtained by the mixture of two variables. One of them follow a binomial distribution  $Bin(2, p)$  with mixing probability  $(1 - \rho)$  and the other one follows a modified Bernoulli distribution,  $MBern(p)$ , taking value 0 and 2 rather than conventional 0 and 1, with mixing probability  $\rho$ :

$$P(Y = y | p, \rho) = (1 - \rho)Bin(2, p)I_{A1} + \rho MBern(p)I_{A2},$$

where  $I_{A1} = \{0, 1, 2\}$ ,  $I_{A2} = \{0, 2\}$  and  $p$  is the probability of success (i.e., acceptable lens fitting).

To overcome the complexity of the mixture likelihood a latent variable  $Z_i, i = 1, 2$  is introduced in the model to indicate in which component of the model the observation  $y_i, i=1, 2$ , belongs to, that is,

$$Z_i = \begin{cases} 1, & \text{if the observation belong to the MBern}(p), \\ 0, & \text{if the observation belong to the Bin}(2, p) \end{cases}$$

The joint distribution of the augmented data  $(Y_i, Z_i), i = 1, 2$ , is given by

$$\begin{aligned} P(Y = y_i, Z = z_i | p, \rho) \\ = \rho^{z_i} p^{y_i z_i / 2} (1 - p)^{(2 - y_i) z_i / 2} (1 - \rho)^{1 - z_i} \binom{2}{y_i} p^{y_i (1 - z_i)} (1 - p)^{(2 - y_i) (1 - z_i)} \end{aligned}$$

The probability  $p$  links to the regression variables through a logit transformation as follow:

$$\text{logit}(p) = \beta_0 + \beta_1 \text{lens}$$

It is assumed that  $\beta_0, \beta_1$  and  $\rho$  to be independent with a non-informative prior  $N(0, 1000)$  for  $\beta_0$  and  $\beta_1$ , and  $\text{beta}(0.5, 0.5)$  for  $\rho$ . The Metropolis sampler algorithm as implemented in the SAS/STAT MCMC Procedure will be used to estimate the posterior distributions of the

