### **Primary Safety Hypothesis 1:**

The null and alternative hypotheses for evaluating superiority of the Test lens relative to 5% are as follows:

$$H_0: p_T \geq 0.05$$
$$H_A: p_T < 0.05,$$

where  $p_T$  is the probability of a Grade 3 or higher SLF across all study visits for Test lens. Based on Bayesian posterior probability distribution of the proportion  $p_T$ , superiority is interpreted as 95% probability of Test being statistically lower than the threshold of 5% (i.e.,  $p_T < 0.05$ ). If the upper bound of the 95% central posterior credible interval is below 0.05, it can be concluded that there is 95% probability that the Test lens is superior to 5% (statistically less than) based on the observed sample.

In the case of zero clinically significant SLF, a Bayesian hierarchical model accounting for zero event problem will be considered.

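### Section 14.1 drops unscheduled visits from all statistical analysis, but Section 2.2 defines both co-primary safety endpoints over scheduled and unscheduled visits

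*Combined protocol and SAP*

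**What the plan says.** Section 14.1 sets a general rule for Section 14: "Unscheduled visits will be summarized separately and will be excluded from the statistical analysis". No exception follows.

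Section 2.2 gives a wider scope for both co-primary safety endpoints. For slit-lamp findings: "Slit Lamp Findings (Grade 3 or higher) will be assessed for each subject eye at all study visits (schedule and unscheduled"; it adds that the percentage of eyes with such findings is what will be analysed. For fit: "Unacceptable lens fit will be assessed at all study visits (scheduled and unscheduled) for each subject eye".

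Other sections use different wordings:

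- Section 2.3, safety hypothesis 1, counts eyes with "at least one reported clinically significant slit-lamp finding (Grade 3 or 4) during the post-fit period".
- Section 14.5, Primary Safety Hypothesis 1, defines a parameter that "is the probability of a Grade 3 or higher SLF across all study visits for Test lens".
- Section 14.5, The Model, defines outcomes "across dispensing and follow-up visits when wearing the Test lens". This text describes lens fit, although it stands under the slit-lamp heading.
- Section 14.5, Primary Safety Hypothesis 2 (fit), names no visits.
- The Table 7 footnote in Section 14.2 says of the historical rates: "Summaries for the primary safety endpoints were provided for the safety population; all available data was included".

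Section 7.3 lists "Slit lamp findings (using the Slit Lamp Classification Scale" among the data collected at an unscheduled visit, as appropriate, and step U.6 provides for biomicroscopy where applicable. Neither the list nor steps U.1 to U.8 include a lens-fit assessment.

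**The concern.** Sections 14.1 and 2.2 cannot both be applied. A Grade 3 or higher finding recorded only at an unscheduled visit is an event under 2.2 and is not one under 14.1. An adverse event is one of the reasons Section 7.3 foresees for such a visit, so a symptomatic problem arising between scheduled visits may well be seen there first.

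The effect runs one way. Leaving visits out can remove slit-lamp events but never add them, so it can only move the upper credible bound down and toward a pass. Sections 2.3 and 14.4 require both safety hypotheses to be met before any efficacy hypothesis is tested, so the visit scope bears on the whole testing sequence. If it stays open, the choice of which events count could be made after they are known, in a single-arm study whose site staff are not masked (Section 5.2).

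Only the count in the formal test is at risk. The findings would still appear in the separate summaries and in adverse event reporting.

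**Working it through.** **Side by side**

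| Place | Visits covered | Unscheduled visits |
|---|---|---|
| 14.1 | all statistical analysis | excluded |
| 2.2, slit lamp | all study visits | included by name |
| 2.2, fit | all study visits | included by name |
| 2.3, hypothesis 1 | post-fit period | not named; inside the period |
| 14.5, hypothesis 1 | all study visits | not named |
| 14.5, model | dispensing and follow-up | not named |
| 14.5, hypothesis 2 | none stated | not named |

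Nothing in 14.5 says that it overrides 14.1, so the conflict is established by the text alone. The arithmetic below only shows how sensitive the test is.

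**Inputs.** From Section 14.5: the two-eye mixture model, logit(p) ~ N(0, 1000), ρ ~ beta(0.5, 0.5), and a pass if the upper limit of the 95% central credible interval for p is below 0.05. From Section 14.2: ρ = 0.70, planning rate 2%, 100 completers, up to 120 enrolled. The 120 case applies if every enrolled subject is exposed to the lens.

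**Model**, for the number of affected eyes Y per subject:

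- P(Y=0) = (1−ρ)(1−p)² + ρ(1−p)
- P(Y=1) = (1−ρ)·2p(1−p)
- P(Y=2) = (1−ρ)p² + ρp

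**The plan's own figure.** Table 8 gives 92.6% power for each safety test. At p = 2%, ρ = 0.70 and n = 100, this model gives 54.5%. The stated figure does not reproduce. That is a separate matter, but it means the sponsor's implementation, and so its exact cut-offs, may differ from those below.

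**Cut-offs** (97.5% posterior quantile of p, grid posterior):

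| n | Events | Upper bound | Result |
|---|---|---|---|
| 100 | 4 one-eye | 4.8% | pass |
| 100 | 5 one-eye | 5.5% | fail |
| 100 | 1 bilateral | 3.2% | pass |
| 100 | 2 bilateral | 5.1% | fail |
| 120 | 5 one-eye | 4.6% | pass |
| 120 | 6 one-eye | 5.2% | fail |
| 120 | 2 bilateral | 4.2% | pass |
| 120 | 3 bilateral | 5.6% | fail |

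Near the boundary, one eye or one bilateral case decides the result. For n = 100 the pass region is at most 4 one-eye cases with no bilateral case, or at most 2 one-eye cases with one bilateral case. Zero events is taken as a pass; the plan uses another model there.

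**Chance of passing when events are dropped.** Let f be the share of affected eyes recorded only at unscheduled visits. The documents give no value, so f = 20%, 30% and 50% are assumptions. The counted rate becomes p(1−f), with ρ held at 0.70.

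Example, true rate 5%, n = 100, f = 0:

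- P(Y=1) = 0.3 × 2 × 0.05 × 0.95 = 0.0285
- P(Y=2) = 0.3 × 0.0025 + 0.7 × 0.05 = 0.03575
- The trinomial sum over the pass region is 0.0217 (no bilateral case) + 0.0425 (one bilateral case) ≈ 6.4%

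With f = 50% the counted rate is 2.5%, P(Y=1) = 0.0146, P(Y=2) = 0.0177, and the sum is 0.165 + 0.247 = 41.2%.

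| True rate | n | f = 0 | 20% | 30% | 50% |
|---|---|---|---|---|---|
| 5% | 100 | 6.4% | 14.6% | 21.2% | 41.2% |
| 5% | 120 | 5.7% | 14.8% | 22.7% | 47.3% |

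At the historical 0.24%, the chance of passing goes from 98.7% to at most 99.7% at n = 100, and from 99.9% to 100.0% at n = 120.

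**The case against.** Four points weigh on the other side.

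1. **Specific over general.** The 14.1 sentence is generic, while the text written for slit-lamp findings in 2.2, 2.3 and hypothesis 1 of 14.5 points to a wide scope. Many statisticians would include unscheduled findings on that reading, and the narrower model wording is really lens-fit text. This makes an oversight the likely explanation. It does not settle the matter, because 14.5 neither names unscheduled visits nor states an exception to 14.1.

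2. **The stand-alone SAP.** Section 14.1 defers detail to a SAP to be finalised before database lock. It may resolve the conflict, but it is not among these documents.

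3. **Most events would be seen again.** Section 8.2 withdraws subjects with a corneal infiltrative event, or with a significant event that requires stopping lens wear, and sends them to a Final Evaluation; step F.3 provides exit biomicroscopy. Subjects who continue are examined at Visits 2 and 3, days apart. An event is lost only if it resolves before the next examination, or if the final examination is missed, waived or not counted. This is a fair point and argues against the high end of the assumed range.

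4. **The 5% scenario is remote.** It is about 20 times the historical rate. The Table 6 safety populations sum to 33 + 44 + 78 + 68 + 75 + 78 + 37 = 413, and 1/413 = 0.24%. Table 7's rate, shown with one eye, therefore looks like a per-subject rate, and per eye it would be about 1/826 = 0.12%. At that rate the test passes with 99.7% to 99.9% probability at n = 100 for any f from 0 to 50%. This stands: if the lens behaves as before, the ambiguity will not change the result.

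Together these lower the likely impact. They do not remove the contradiction.

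**Conclusion.** The concern holds: the plan is wrong as written. Section 14.1 contradicts 2.2 on which visits count for both co-primary safety endpoints, and no passage says which prevails. The practical exposure is confined to slit-lamp findings recorded only at unscheduled visits, and it can only favour passing.

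Its size depends on the true rate. It is negligible near the historical rate. At a true rate of 5% it is material: the chance of wrongly passing at n = 100 roughly doubles (14.6 / 6.4 = 2.3) if 20% of affected eyes are missed, and is 41.2% if half are. These figures rest on the 14.5 model with its stated priors, ρ = 0.70 and assumed shares. The conflict itself rests on none of them. If 2.2 is meant to govern, nothing is lost.

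For fit there is a separate gap in collection: 2.2 promises an assessment at unscheduled visits that the Section 7.3 procedures do not list. This should be fixed before database lock.

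**What to change.** - **Section 14.1:** add one sentence saying that the exclusion of unscheduled visits does not apply to the co-primary safety endpoints.
- **Section 14.5** (the model text and both safety hypotheses): state one visit scope that matches 2.2 and 2.3. A Grade 3 or higher slit-lamp finding counts if recorded at any post-fit scheduled, unscheduled or final/exit evaluation. An unacceptable fit counts if recorded at any scheduled or unscheduled visit where fit is assessed. Carry the same wording into the stand-alone SAP.
- **Section 7.3:** reconcile the unscheduled-visit procedures, which contain no fit assessment, with the fit endpoint in 2.2.

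The cost is a few sentences and no extra subjects. The observed event rate may be slightly higher than under the literal 14.1 rule.

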# Clinical Study Protocol

## Johnson & Johnson Vision Care, Inc.

- Chronic disease
- Foetal distress, foetal death or a congenital physical or mental impairment of birth defect.

Diagnoses and conditions that are considered Ocular Serious Adverse Events include, but not limited to:

- Microbial Keratitis (MK)
- Iritis (including cells in the anterior chamber)
- Permanent decrease in best spectacle corrected visual acuity equivalent to 2 acuity lines or greater
- Central Corneal Opacity
- Central Corneal Neovascularization
- Uveitis
- Endophthalmitis
- Hypopyon
- Hyphemia
- Penetration of Bowman's Membrane
- Persistent Epithelial Defect
- Limbal cell Damage leading to Conjunctivalization

**Significant Adverse Events** – are defined as events that are symptomatic and warrant discontinuation (temporary or permanent) of the contact lens wear

Diagnoses and conditions that are considered Ocular Significant Adverse Events include, but not limited to the following:

- Contact Lens Induced Peripheral Ulcer (CLPU)
- Significant Infiltrative Events (SIE)
- Superior Epithelial Arcuate Lesions (SEALs)
- Any Temporary Loss of > 2 Lines of BSCVA
- Other grade 3 or higher corneal findings, such as abrasions or edema
- Non-contact lens related corneal events - e.g. Epidemic Keratoconjunctivitis (EKC)
- Asymptomatic Corneal Scar
- Any corneal event which necessitates temporary lens discontinuation > 2 weeks

**Non-Significant Adverse Events** – are defined as those events that are usually asymptomatic and usually do not warrant discontinuation of contact lens wear but may cause a reduction in wear time. However, the Investigator may choose to prescribe treatment as a precautionary measure.

Diagnoses and conditions that are considered Ocular Non-Significant Adverse Events include, but not limited to the following:

- Non-significant Infiltrative Event (NSIE)
- Contact Lens Papillary Conjunctivitis (CLPC)
- Superficial Punctate Keratitis (SPK)

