# Clinical Study Protocol

## Johnson & Johnson Vision Care, Inc.

- Conjunctivitis: Bacterial, Viral, Allergic
- Blepharitis
- Meibomianitis
- Contact Dermatitis
- Localized Allergic Reactions
- Any corneal event not explicitly defined as serious or significant adverse event, which necessitates temporary lens discontinuation < 2 weeks

**Adverse Device Effect (ADE)** – An ADE is an “adverse event related to the use of an investigational medical device.”

**NOTE 1: This definition includes adverse events resulting from insufficient or inadequate instructions for use, deployment, implantation, installation, or operation, or any malfunction of the investigational medical device.**

**NOTE 2: This definition includes any event resulting from use error or from intentional misuse of the investigational medical device.**

**Unanticipated Adverse Device Effect (UADE)** – A UADE is any serious adverse effect on health or safety or any life-threatening problem or death caused by, or associated with, the test article, if that effect, problem, or death was not previously identified in nature, severity, or degree of incidence in the investigational plan, Investigator’s Brochure or protocol, or any other unanticipated serious problem associated with the test article that relates to the rights, safety and welfare of subjects.

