Subjects who present with an adverse event shall be followed by the Investigator, within licensure, until all signs and symptoms have returned to pre-treatment status, stabilized, or been satisfactorily resolved. If further treatment beyond licensure is required, the patient will be referred to the appropriate health care provider. The Investigator will use his/her clinical judgment as to whether a subject reporting with an adverse event will continue in the study. If a subject is discontinued from the study, it will be the responsibility of the Investigator to record the reason for discontinuation. The Investigator will also document the adverse event appropriately and complete the Adverse Event eCRF. Any subjects with ongoing adverse events related to the test article, study treatment or study procedures, as of the final study visit date, should be followed to resolution of the adverse event or until referral to an appropriate health care provider, as recommended by the Investigator. Non-ocular adverse events that are not related to the test article, study treatment, or study procedures may be recorded as “ongoing” without further follow-up.

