### Primary Safety Endpoint Sample Size Calculations:

#### Grade 3 or Higher Slit Lamp Findings (SLF) and Unacceptable Lens Fitting

Sample size estimates for SLFs grade 3 or higher and unacceptable lens fitting were calculated using the same technique and assumptions. Since both safety endpoints are testing against a 5% threshold and have an event rate less than 0.5% both endpoints require the same sample to achieve the same pre-specified confidence level of 95%. Furthermore, it should be noted that why both endpoints are collected on all subjects they are clinically independent.

For Grade 3 or Higher SLF was converted to a binary response as  $Y = 1$  if a subject eye has a clinically significant SLF and  $Y = 0$  otherwise for analysis purpose (Unacceptable lens fitting is derived as a binary response as  $Y=1$  is a subject had an unacceptable lens fit and 0 otherwise). From the historical data there was no/extremely low rate ( $< 1\%$ ) for clinically significant SLFs (Grade 3 or higher) or unacceptable lens fitting for the study lens. Assuming a correlation of 0.70 between left and right eyes within the same subject, a total of 2000 replicating trials were simulated with a reference rate of 2% (worse-case scenario). Given the rare event binary outcome of slit lamp findings, (or unacceptable lens fit) each replicated sample was analyzed using a Bayesian beta-binomial model with correlated binary data (Diniza et al; 2010). For each simulated trial, the upper bound of the 95% central posterior credible interval constructed for the percentage of Grade 3 or higher SLFs for the Test lens was compared to a margin of 5%. With the proposed sample size, there was at least 90% of the estimated 95% credible intervals with the upper bound being below 5%.

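### Section 14.1 excludes unscheduled visits from the statistical analysis with no safety exception, although Section 2.2 counts the co-primary slit-lamp endpoint at those visits

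*Combined protocol and SAP*

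**What the plan says.** The general rule in Section 14.1 is: "Unscheduled visits will be summarized separately and will be excluded from the statistical analysis". No endpoint is exempted.

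The endpoint text is wider:

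- Section 2.2 says: "Slit Lamp Findings (Grade 3 or higher) will be assessed for each subject eye at all study visits (schedule and unscheduled".
- Section 2.3 counts an eye with at least one "clinically significant slit-lamp finding (Grade 3 or 4) during the post-fit period".
- Section 14.5, Primary Safety Hypothesis 1, says that p_T "is the probability of a Grade 3 or higher SLF across all study visits for Test lens". It does not name unscheduled visits.
- The model paragraph in 14.5, under the slit-lamp heading but worded for lens fit, refers to outcomes at dispensing and follow-up visits.
- Section 14.2 codes Y = 1 "if a subject eye has a clinically significant SLF" and Y = 0 otherwise.

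Slit-lamp findings are among the data listed for unscheduled visits (Section 7.3). Both safety hypotheses must be met before any efficacy hypothesis is tested (Sections 2.3 and 14.4). Section 14.1 defers detail to a stand-alone SAP, and nothing in the documents settles which text prevails.

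**The concern.** The two rules give different data sets for the same co-primary test. An eye whose only Grade 3 or higher finding was recorded at an unscheduled visit is an event under 2.2. Under 14.1 it is not.

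The difference runs one way. Leaving such visits out can only remove events, which lowers the upper credible bound and makes a pass more likely. This test opens the gate to every efficacy claim, so a single affected subject near the boundary could decide whether efficacy is tested at all.

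**Working it through.** **Can an event exist only on an unscheduled form?** Yes, by this route. Between Visits 2 and 3, which are 7±1 days apart, a subject comes in unscheduled with a Grade 3 conjunctival finding. Section 13.1 lists "Conjunctivitis: Bacterial, Viral, Allergic" among the non-significant events, which "usually do not warrant discontinuation of contact lens wear but may cause a reduction in wear time". Section 13.3 adds: "The Investigator will use his/her clinical judgment as to whether a subject reporting with an adverse event will continue in the study". If the subject stays in and the eye is clear at Visit 3, the exit slit-lamp step F.3 does not apply, since it is for early discontinuations. The eye is then Y = 1 under 2.2 and Y = 0 under 14.1. If instead the event came before Visit 2 and the subject left without a counted examination, the eye may be missing rather than 0, because Section 14.9 imputes nothing.

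**Inputs.** From Sections 14.2 and 14.5: 100 completers, correlation ρ = 0.70, planning rate 2% of eyes, limit 5%, prior N(0,1000) on the logit coefficients and beta(0.5,0.5) on ρ. The test passes if the 97.5% posterior quantile of p is below 0.05. The historical rate is 0.24% (Table 7). The share f of affected subjects seen only at unscheduled visits is not given; 10%, 25% and 50% are assumptions.

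**Model (14.5), per subject:**

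- P(one eye) = 2(1−ρ)p(1−p)
- P(both eyes) = (1−ρ)p² + ρp

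With one lens, logit(p) reduces to a single parameter. Doubling its prior variance to 2000 moves the bounds by at most 0.01 point. Zero events are taken as a pass.

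**The plan's own figure.** Table 8 gives 92.6% power at these inputs. The model of 14.5 gives 54.5%, so I could not reproduce it. That is a separate question. The comparisons below use the 14.5 model throughout.

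**Upper bounds from the posterior:**

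| Subjects | Affected subjects | Upper bound | Result |
|---|---|---|---|
| 100 | 5 single-eye | 5.51% | fail |
| 100 | 4 single-eye (one dropped, scored 0) | 4.79% | pass |
| 99 | 4 single-eye (one dropped, missing) | 4.84% | pass |
| 100 | 2 bilateral | 5.08% | fail |
| 100 | 1 bilateral (one dropped, scored 0) | 3.21% | pass |
| 120 | 2 bilateral | 4.24% | pass |
| 120 | 6 single-eye | 5.18% | fail |
| 120 | 5 single-eye (one dropped, scored 0) | 4.60% | pass |

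One subject can reverse the result at either size, but the boundary sits in a different place.

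**Pass probability, n = 100.** The passing outcomes are no bilateral subject with at most four single-eye subjects, or one bilateral with at most two single-eye. Multiply both cell probabilities by (1−f) and sum the multinomial over those outcomes. At p = 0.02:

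- P(one eye) = 2 × 0.3 × 0.02 × 0.98 = 0.01176
- P(both eyes) = 0.3 × 0.0004 + 0.7 × 0.02 = 0.01412
- with f = 0.25 these become 0.00882 and 0.01059

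| True rate | All visits count | f = 10% | f = 25% | f = 50% |
|---|---|---|---|---|
| 0.24% | 98.7% | 99.0% | 99.3% | 99.7% |
| 2% | 54.5% | 60.3% | 69.1% | 83.5% |
| 5% | 6.4% | 9.8% | 17.6% | 41.0% |

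These score dropped eyes as 0. If the dropped subjects are missing instead, the f = 25% column reads 99.3%, 66.3% and 13.6%. At n = 120, a true 5% rate and f = 25% scored 0, the move is from 5.7% to 18.5%.

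**The case against.** **The specific text should govern.** Section 14.1 is a general description and 2.2 is the endpoint definition. The Table 7 footnote says the historical safety summaries used all available data. Counting unscheduled visits is the better reading. But no sentence says 2.2 overrides 14.1, Section 14.10 commits the analysis to the sections above it, and a programmer who filters out unscheduled records is following a written instruction.

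**The SAP may settle it.** It may, and it is not in the documents. It need only be final before database lock, however. The study has one arm, and adverse events reach the sponsor within 24 hours or 2 days (Section 13.4), so the counting rule could be fixed with events already known.

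**Most such events are captured anyway.** This largely stands. Section 8.2 withdraws subjects with a corneal infiltrative event, with a significant or serious event that requires stopping lens wear, or who no longer meet eligibility. Exclusions 7, 14 and 15 cover ocular medication, Grade 2 or greater findings, and current infection or inflammation. Exclusions 14 and 15 are baseline criteria and 13.3 leaves discretion, so keeping the subject in the worked case is arguable, but withdrawal is at least as likely. Withdrawal leads to the Final Evaluation, where F.3 would naturally record the finding again. What remains is a finding that appears and clears between closely spaced visits in a subject who stays in, or a withdrawn subject whose F.3 examination is skipped or not counted.

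**Readings that go too far.** A reader might infer that 14.5 itself counts unscheduled visits; only 2.2 names them. A reader might also infer that safety events would be hidden. They would still appear in the separate unscheduled summary and in adverse-event reporting; only the formal test is affected.

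**Conclusion.** The conflict is real, and 14.1 is wrong as written for this endpoint. Followed literally, it drops a Grade 3 or higher finding recorded only at an unscheduled visit from a gatekeeping test, always in the lens's favour.

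The size depends on the true rate and on an unscheduled-only share that the documents do not give. At 0.24% the effect is 0.6 points for a 25% share (99.3 − 98.7). For the same share it is 14.6 points at 2% (69.1 − 54.5) and 11.2 points at 5% (17.6 − 6.4).

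Two inferences are not supported. One is that the conflict matters only for a lens near or above 5%. That holds for a false pass, which needs a true rate of at least 5%, but the test result shifts at the plan's own 2% rate too. The other is that the false-pass risk will reach figures such as 41.0%. That needs half of affected subjects to be seen only at unscheduled visits, and the withdrawal rules make such cases uncommon.

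Confidence is high on the wording conflict. It is not high that an event would in fact be lost.

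**What to change.** In Section 14.1, add to the sentence on unscheduled visits: *except for the co-primary slit-lamp safety endpoint, which includes all scheduled and unscheduled visits.*

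In Section 14.5 and the SAP, state that each eye takes its worst slit-lamp grade at any examination after first lens insertion through the Final Evaluation, including unscheduled visits and exit biomicroscopy. Let this replace the visit wording of the model paragraph for this endpoint.

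The cost is one clause and one derivation rule, using data already listed for collection. The downside is that more events count, so an acceptable lens passes less often. With a 25% share scored 0, the pass probability falls from 97.1% to 95.1% at a true 0.5% rate, and from 69.1% to 54.5% at 2%. The lower figures are what the Section 2.2 definition implies.

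A separate, minor alignment: Section 2.2 also promises lens-fit assessment at unscheduled visits, but steps U.1 to U.8 contain none. Either remove the word there or record fit when lenses are worn to the visit.
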